#### 5.2 **Exclusion criteria**

- More than 6 months of cumulative iron chelation therapy (such as daily deferasirox (Exjade®) or deferiprone or 5×/week deferoxamine)
  - Intermittent deferoxamine doses in association with blood transfusions are not exclusionary regardless of duration of such treatment
- More than 3 years since patient began receiving regular transfusions (2 units per 8 weeks or 4 units received in a 3 month period)
- Creatinine Clearance <40 ml/min

- Serum creatinine  $> 1.5 \times ULN$  at screening
  - Serum creatinine will be measured at Screening Visit 1 and Screening Visit 2 (at least 14 days apart) and the mean value will be used for eligibility criteria.
- Significant proteinuria as indicated by a urinary protein/creatinine ratio > 0.5 mg/mg in a non-first void urine sample at Visit 1 or Visit 2 (or alternatively in two of three samples obtained for screening)
- ECOG performance status > 2
- Left ventricular ejection fraction < 50% by echocardiography as per the central reading assessment
- A history of hospitalization for congestive heart failure
- Systemic diseases which would prevent study treatment (e.g. uncontrolled hypertension, cardiovascular, renal, hepatic (including Child-Pugh Class B and C), metabolic, etc.)
- Clinical or laboratory evidence of active Hepatitis B or Hepatitis C (HBsAg in the absence of HBsAb OR HCV Ab positive with HCV RNA positive)
- History of HIV positive test result (ELISA or Western blot)
- Treatment with systemic investigational drug within 4 weeks or topical investigational drug within 7 days of study start
- ALT or AST  $> 3.5 \times ULN$  at screening
- Total bilirubin  $> 1.5 \times ULN$  at screening
- Diagnosis of liver cirrhosis (either established diagnosis or diagnosis by liver biopsy or central ultrasound reading)
- Patients participating in another clinical trial other than an observational registry study
- Patients with a history of another malignancy within the past five years, with the exception of basal skin carcinoma or cervical carcinoma *in situ* or completely resected colonic polyps carcinoma *in situ*.
- History of non-compliance to medical regimens, or patients who are considered potentially unreliable and/or not cooperative
- Presence of a surgical or medical condition which might significantly alter the absorption, distribution, metabolism or excretion of study drug

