#### 6.7.1.3 Elevations in serum creatinine

For patients who develop an increase in serum creatinine  $\ge 33\%$  above their baseline value (the mean value established at screening Visits 1 and 2) resulting in a serum creatinine above the ULN, on two consecutive occasions, a minimum of 7 days apart, the daily dose will be reduced by 10 mg/kg (or 5 mg/kg in patients receiving 10 mg/kg).

If, after a dose reduction, serum creatinine remains above the ULN, a second dose reduction or treatment interruption is recommended. After an interruption, if serum creatinine falls below the age appropriate ULN on two consecutive visits, the investigator may resume therapy at 50% of the last dose and escalate cautiously.

Serum creatinine should be monitored weekly, preferably by local labs, for the first month after study drug initiation or dose modification. Results of these labs need to be entered into the CRF only if they are significantly abnormal, defined as at least a 33% increase over the baseline value.

If after dose reduction, a progressive increase in serum creatinine is observed, study drug may be discontinued if the investigator believes it is in the best interest of the patient. Novartis may be contacted by the investigator to discuss dosing options if the investigator so desires.

Caution should especially be used in patients with creatinine clearance between 40 and less than 60 mL/min, particularly in cases where there are additional risk factors that may impair renal function such as concomitant medications, dehydration, or severe infections.

Protocol No. CICL670A2302

Study medication should be discontinued in case serum creatinine increases >2 times the age-appropriate upper limit or if creatinine clearance <40 mL/min.

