#### Reporting of laboratory data

The following by-treatment summaries will be generated separately for hematology, biochemistry and urinary laboratory tests:

- Frequency table for newly occurring on-treatment grades 3 or 4.
- Shift tables using CTCAE grades to compare baseline to the worst on-treatment value.
- For laboratory tests where CTCAE grades are not defined, shift tables using the low/normal/high/(low and high) classification to compare baseline to the worst ontreatment value.

For a specific laboratory test, patients with newly occurring on-treatment grade 3 or 4 are defined as:

- Patients with baseline grade missing, 0, 1 or 2 and worst on-treatment grade 3 or 4 (percentage to be based on all patients with baseline grade missing, 0, 1 or 2).
- Patients with baseline grade missing, 0, 1, 2 or 3 and worst on-treatment grade 4 (percentage to be based on all patients with baseline grade missing, 0, 1, 2 or 3).

The following listings will be generated:

- Listing of laboratory data for patients with newly occurring grade 3 or 4 laboratory toxicities.
- Listing of laboratory data for patients with values outside the laboratory normal ranges with values flagged to show the corresponding CTCAE grades and the classifications relative to the laboratory normal ranges.
- Listing of all laboratory data with values flagged to show the corresponding CTCAE grades and the classifications relative to the laboratory normal ranges.

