2.8.3 Laboratory data

All laboratory values are generally converted into SI units and the severity grade calculated using notable and extended ranges as available in the deferasirox program standards. All values from central laboratory will be used to evaluate the primary and secondary endpoints. Any tests that are performed at local laboratories will not be used for either secondary or primary endpoints evaluation; however, collected local laboratory values will be listed along with central laboratory results and also for safety tables, all values for central and local laboratory results will be considered.

The frequency of laboratory abnormalities is displayed by parameter and treatment group. Laboratory data is summarized by presenting summary statistics of raw values and absolute and relative change from baseline.

Shift tables from baseline to highest (or lowest) post baseline value are provided for hematology: hemoglobin, WBC count, absolute neutrophils and platelets, biochemistry: alanine aminotransferase (ALT), aspartate aminotransferase (AST), serum creatinine and creatinine clearance and urinalysis: urinary total protein/creatinine ratio using normal or extended ranges. Standard oncology shift tables for laboratory parameters, based on normal ranges, are also provided.

Box plots of absolute value and the absolute change from baseline in absolute neutrophils, platelets, ALT, AST, serum creatinine, creatinine clearance and urinary total protein/creatinine ratio by time points are provided. The last available value in a time point window is used.

Criteria for clinically notable and extended laboratory ranges

Parameter	Criteria
Absolute neutrophils	<1.5×10 ⁹ /L (extended range <0.5×10 ⁹ /L)
Platelets	<100×10 ⁹ /L (extended range <50×10 ⁹ /L)
ALT/AST	>5×ULN and >2×baseline value (extended range >10×ULN and >2×baseline value)
Serum creatinine	>33% increase from baseline and >ULN at two consecutive measurements at least 7 days apart
Creatinine clearance	<60 mL/min at two consecutive measurements at least 7 days apart (extended range <40 mL/min)
Urinary total protein/creatinine ratio	>1.0 mg/mg at two consecutive measurements at least 7 days apart
Total bilirubin	>2.0 mg/dL (>34.2 umol/L)

The number and percentage of patients with laboratory results (from scheduled and unscheduled visits) meeting the criteria for notable values (see table above) will be presented.

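### The notable creatinine-clearance row in SAP 2.8.3 has no baseline condition, so stable clearance of 40–59 mL/min at entry is counted as an on-treatment notable value

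*SAP*

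**What the plan says.** The table of clinically notable ranges in SAP section 2.8.3 defines the clearance row as "<60 mL/min at two consecutive measurements at least 7 days apart (extended range <40 mL/min". The text below the table says that counts and percentages of patients with results "meeting the criteria for notable values (see table above) will be presented". Neither place restricts the row by baseline clearance.

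At entry, protocol section 5.2 excludes "Creatinine Clearance <40 ml/min" and sets no higher limit. Protocol section 6.7.1.3 recognises patients in the gap: "Caution should especially be used in patients with creatinine clearance between 40 and less than 60 mL/min".

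Other parts of the plan do take baseline into account. In the same SAP table, serum creatinine is notable at ">33% increase from baseline and >ULN at two consecutive measurements at least 7 days apart" and ALT/AST at ">5×ULN and >2×baseline value". For newly occurring CTCAE grades, protocol section 10.5.2.4 counts "Patients with baseline grade missing, 0, 1 or 2 and worst on-treatment grade 3 or 4" and restricts the denominator to match: "percentage to be based on all patients with baseline grade missing, 0, 1 or 2".

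**The concern.** The clearance threshold of 60 lies inside the eligible range. A patient who is randomized at 50 mL/min and never changes meets the criterion in either arm. The row therefore mixes impairment that was present before treatment with decline on treatment, and only the second bears on the drug.

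Protocol section 1.3 lists dose-dependent creatinine increases and rare acute renal failure among the known effects of deferasirox, and section 3.2 names laboratory abnormalities in the safety objective. That objective is to exclude unacceptable increases in risk. A row whose ratio is expected to drift toward 1 when there is a real effect errs in the less cautious direction.

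Among the renal rows this problem is specific to clearance. The creatinine row is relative to baseline. The urinary protein/creatinine limit (above 1.0 mg/mg) lies above the corresponding exclusion limit (above 0.5 mg/mg).

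**Working it through.** The plan states no figure for this row, so there is nothing to reproduce. The check is algebra on assumed inputs.

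**Inputs.** From the documents: threshold 60 mL/min confirmed twice (SAP 2.8.3), exclusion below 40 (protocol 5.2), 210 patients at 2:1, hence 140 and 70. Assumed, with no source in the documents: q, the share with baseline clearance 40–59; f, the share of those who are flagged on treatment; d and p, the new-onset risks on deferasirox and placebo among patients with baseline of at least 60.

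**Formula.** Tabulated rate per arm = q·f + (1 − q)·risk. With f = 1 in both arms, the tabulated ratio is [q + (1 − q)d] / [q + (1 − q)p]. Among patients at risk the ratio is d/p, whatever q is.

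**d = 0.45, p = 0.20, f = 1 (true ratio 2.25, true difference 0.25).**

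| q | deferasirox | placebo | ratio | difference |
|---|---|---|---|---|
| 0.20 | 0.20 + 0.80×0.45 = 0.560 | 0.20 + 0.80×0.20 = 0.360 | 1.56 | 0.200 |
| 0.30 | 0.30 + 0.70×0.45 = 0.615 | 0.30 + 0.70×0.20 = 0.440 | 1.40 | 0.175 |
| 0.40 | 0.40 + 0.60×0.45 = 0.670 | 0.40 + 0.60×0.20 = 0.520 | 1.29 | 0.150 |
| 0.50 | 0.50 + 0.50×0.45 = 0.725 | 0.50 + 0.50×0.20 = 0.600 | 1.21 | 0.125 |

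**Other assumed risks.** With 30% vs 15% (true ratio 2.0) and f = 1, the ratio is 0.44/0.32 = 1.38 at q = 0.20 and 0.65/0.575 = 1.13 at q = 0.50. With 20% vs 10% (true ratio 2.0), q from 10% to 40% and f from 0.8 to 1.0, it lies between 1.53 and 1.13.

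**Unequal flagging.** Suppose deferasirox also keeps more of the 40–59 group below 60: f = 0.95 against 0.80 on placebo, q = 0.20, new-onset 20% vs 10%. The rates are 0.20×0.95 + 0.80×0.20 = 0.35 and 0.20×0.80 + 0.80×0.10 = 0.24. The ratio is 1.46 against a true 2.0. The difference is 0.11 against a true 0.10, so it does not shrink. With placebo f of 0.7–0.8, deferasirox f of 0.95 and q of 10–30%, the ratio is 1.37–1.72 and the difference 0.105–0.145.

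**Chance imbalance.** In 200,000 simulated trials per setting (140 vs 70 patients, 20% vs 10%, f = 1, q of 10–30%), the all-patient ratio was closer to 1 than the at-risk ratio in 88–93%. In the rest it was not.

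**Is baseline clearance of 40–59 plausible here?** By the Cockcroft-Gault formula in SAP 5.3.1, a 75-year-old man of 70 kg has clearance 65×70/(0.815×SCr) = 5583/SCr. That equals 60 at a creatinine of about 93 µmol/L and 40 at about 140 µmol/L. This shows how such a patient can arise, not how many there are.

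**The case against.** The strongest reply is that this is one descriptive row among seven. SAP 2.8.3 promises a count and a percentage for it, and neither document specifies a risk ratio for clearance below 60. The protocol synopsis plans risk ratios for pre-specified adverse events but does not extend them to this row. Absolute thresholds are also the table's usual form: neutrophils, platelets, urinary protein/creatinine and total bilirubin have no baseline condition either. The denominator is not spelled out, since SAP 2.1.1 refers only to the relevant population or subgroup. All of this stands, and it limits the point to how the row will be read.

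The SAP also plans a baseline-to-lowest shift table for clearance, box plots of change, and summary statistics of change from baseline. These help a reader separate old impairment from new decline, but only in part. The shift table uses the single lowest value, so confirmed new onset below 60 cannot be read from it, and box plots do not count patients who cross a threshold. The below-40 range coincides with the entry limit and is therefore effectively treatment-emergent already for eligible patients.

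It is fair, too, that equal flagging in both arms is an assumption, and that the assumed risks have no source. The neutrophil and platelet rows are a weaker parallel, because SAP 2.8 gives those parameters a separate endpoint for newly occurring cases. Clearance has none.

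**Conclusion.** The omission is real and small in scope. Stable pre-existing clearance of 40–59 mL/min is counted as notable. If the drug lowers clearance, the ratio read from this row is expected to lie nearer to 1 than the ratio for new decline. The range 1.56 to 1.21 for a true 2.25 illustrates the algebra under the stated assumptions. It does not measure the problem in this trial, because the 40–59 share and the event rates are unknown. The direction is an expectation for the ratio only: the risk difference need not shrink, and chance imbalance can go either way in a single trial.

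A reader might infer that the trial's renal safety comparison as a whole is pulled toward no difference. The documents do not support that. The pre-specified renal endpoint (SAP 2.8, protocol 10.5.2.2) is serum creatinine of at least 2 times ULN at two consecutive assessments. It carries the planned 95% confidence interval and does not use clearance. The notable creatinine row already requires a rise from baseline.

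**What to change.** In SAP 2.8.3, tabulate confirmed clearance below 60 mL/min as newly occurring, with numerator and denominator limited to patients whose baseline clearance is at least 60 or missing. This follows protocol 10.5.2.4, which keeps patients with a missing baseline. State that the safety baseline of SAP 2.1.2.8 (last assessment on or before the start of treatment) applies, because the same section also defines a screening mean for clearance under efficacy evaluations. Show patients with baseline 40–59 as a separate row, and keep the existing below-40 range for all patients, which also shows further decline in that group.

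No new data are needed; clearance is already collected at screening and at every visit. The cost is a denominator smaller by the factor (1 − q). At q = 0.20, 140 and 70 become 112 and 56, and for a given percentage the standard error rises by 1/√0.80 = 1.12, or about 12%. At q = 0.50 it would rise by 1/√0.50 = 1.41, or about 41%.

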2.8.4 Other safety data

2.8.4.1 ECG and cardiac imaging data

2.8.4.1.1 Data handling

In case the study requires ECG replicates at any assessment, the average of the ECG parameters at that assessment should be used in the analyses.

2.8.4.1.2 Data analysis

12-lead ECGs with PR, QRS, QT, QTcF, QTcB, and HR intervals will be obtained for each subject during the study. ECG data will be read and interpreted centrally.

The number and percentage of subjects with notable ECG values will be presented by treatment arm.

• QT, QTcF and QTcB

- New value of >450 and ≤ 480 ms
- o New value of >480 and <500 ms
- o New value of >500 ms
- Increase from baseline of >30 ms to ≤ 60 ms
- o Increase from baseline of >60 ms

HR

- o Increase from baseline >25% and to a value >100 bpm
- o Decrease from baseline >25% and to a value <50 bpm

PR

- o Increase from baseline >25% and to a value >200 ms
- o New value of >200 ms

- QRS
 - o Increase from baseline >25% and to a value >120 ms
 - o New values of QRS >120 ms

A listing of all ECG assessments will be produced by treatment arm and notable values will be flagged. A separate listing of only the subjects with notable ECG values may also be produced. In the listing, assessments collected during the post-treatment period will be flagged.

2.8.4.2 Vital signs

Vital sign assessments are performed in order to characterize basic body function. The following parameters are collected: height (cm), weight (kg), body temperature (°C), respiratory rate (beats per minute), sitting systolic and diastolic blood pressure (mmHg).

The change from baseline in systolic and diastolic blood pressures, respiratory rate, temperature and weight will be summarized by scheduled visit with n, mean, SD, median, minimum and maximum values.

A listing will be provided for all vital signs and BMI (Body Mass Index). Notable vital signs are flagged. The criteria for notable abnormal vital signs are displayed in Table 2-1.

Table 2-1 Definition of notable ranges for blood pressure and weight

Parameter	Criteria for notable ranges
Systolic blood pressure	≥ 180 mmHg / ≤ 90 mmHg with increase / decrease from baseline ≥ 20 mmHg
Diastolic blood pressure	≥ 105 mmHg / ≤ 50 mmHg with increase / decrease from baseline ≥ 15 mmHg
Weight	≥ 10% increase or decrease from baseline weight

2.8.4.3 Auditory and ophthalmic findings

Auditory and ophthalmic overall interpretation data will be summarized using shift tables comparing baseline result to most extreme post-baseline value.

Auditory data will be listed using the Safety set. The listing will include when tests are performed, overall interpretation, and any clinical significant abnormality findings.

Ophthalmic data includes visual acuity, slit lamp findings, tonometry, and fundus oculi. Results will be listed by test date using Safety Set.

2.9 Pharmacokinetic endpoints

Not applicable.

2.10 Patient-reported outcomes

Not applicable.

2.11 Biomarkers

Not applicable.

2.12 Other Exploratory analyses

No exploratory analyses are planned for this study.

2.13 Interim analysis

No interim analysis will be performed.

3 Sample size calculation

The sample size of 210 patients randomized in a ratio of 2:1 in favor of deferasirox is based on the feasibility of enrolling the patients and consultations with the Health Authorities. As noted earlier, this study is not powered for any confirmatory primary or secondary endpoints.

4 Change to protocol specified analyses

The following change was made:

• Newly occurring thrombocytopenia and neutropenia was redefined using the definition of the corresponding notable laboratory abnormalities

5 Appendix

5.1 Imputation rules

5.1.1 Study drug

The following rule will be used for the imputation of date of last administration for a given study treatment component.

Case 1: The date of last administration is completely missing, and the EOT visit date is complete, then this latter date should be used.

Case 2: Only Year (yyyy) of the dose end date is available and yyyy < the year of EOT date:

Impute date= Dec31yyyy

Case 3: Only Year (yyyy) of the dose end date is available and yyyy = the year of EOT date:

Impute date=EOT date

Case 4: Both Year (yyyy) and Month (mm) are available for the date of last administration, and yyyy = the year of EOT date and mm < the month of EOT visit:

Impute date= last day of the Month (mm).

After imputation, compare the imputed date with the start date of that specific record, if the imputed date is < start date of that record

Impute date= the start date of that record.

Subjects with missing start dates will be considered missing and no imputation will be made. If the date of first administration is missing, then the date of last administration should not be imputed.

5.1.2 AE date imputation

Date imputation is the creation of a new, complete date from a partial one according to an agreed and acceptable algorithm. The missing date for AEs will be handled according to STL (Standard Tables and Listings) standard.

A partial date is simply an incomplete date e.g., ddOCT2001 the days are missing from this DDMMMYYYY date.

Partial adverse event start dates, if left partial, will ultimately mean the following It will not be possible to place the adverse event in time.

Therefore, the treatment/dosage at the time of the event will be unknown.

Therefore, the event could not be reported/summarized appropriately - if at all.

There will be no attempt to impute the following

- Missing AE start dates
- AE start dates missing the year
- Partial/missing AE end dates

Table 5-1 AE/treatment date abbreviations

	Day	Month	Year
Partial AE start date	<not used=""></not>	AEM	AEY
Treatment start date (TRTSTD)	<not used=""></not>	TRTM	TRTY

The following matrix Table 5-2 describes the possible combinations and their associated imputations. In the light grey boxes the upper text indicates the imputation and the lower text is the relationship of the AE start date to the treatment start date (TRTSTD).

Table 5-2 AE partial date imputation algorithm

	AEM Missing	AEM < TRTM	AEM = TRTM	AEM > TRTM
AEY Missing	NC	NC	NC	NC
	Uncertain	Uncertain	Uncertain	Uncertain
	(D)	(C)	(C)	(C)
AEY < TRTY	Before TRTSTD	Before TRTSTD	Before TRTSTD	Before TRTSTD
	(B)	(C)	(B)	(A)
AEY = TRTY	Uncertain	Before TRTSTD	Uncertain	After TRTSTD
	(E)	(A)	(A)	(A)
AEY > TRTY	After TRTSTD	After TRTSTD	After TRTSTD	After TRTSTD
	(E)	(A)	(B)	(A)

Table 5-3 AE/treatment date relationship and imputation

Novartis	For business use only	Page 38
RAP M3 Amendment 4		ICL670A2302

Relationship	
Before TRTSTD	Indicates AE start date prior to Treatment Start Date
After TRTSTD	Indicates AE start date after Treatment Start Date
Uncertain	Insufficient to determine the relationship of AE start date to
	Treatment Start Date
Imputation Calculation	
NC/Blank	No convention/imputation
(A)	01MONYYYY
(B)	TRTSTD+1
(C)	15MONYYYY
(D)	01JULYYYY
(E)	01JANYYYY

The following Table 5-4 gives a few examples.

Table 5-4 Example Scenarios

Partial AE start	Treatment start	Relationship	Imputation	Imputed date
date	date		calculation	
12mmyyyy	20OCT2001	Uncertain	NC	<black></black>
ddmmm2000	20OCT2001	Before	(D)	01JUL2000
ddmmm2002	20OCT2001	After	(E)	01JAN2002
ddmmm2001	20OCT2001	Uncertain	(B)	21OCT2001
ddSEP2001	20OCT2001	Before	(C)	15SEP2001
ddOCT2001	20OCT2001	Uncertain	(B)	21OCT2001
ddNOV2001	20OCT2001	After	(A)	01NOV2001

5.1.3 Concomitant medication date imputation

The imputation of the start date of concomitant medication will follow the same convention as for the AE date. A partial concomitant medication end date will not be imputed.

5.1.3.1 Prior therapies date imputation

Start date:

The same rule which is applied to the imputation of AE/concomitant medication start date will be used with the exception that for scenario (B) will be replaced to be 'start date of study drug -1'.

End date:

Imputed date = min (start date of study drug, last day of the month), if day is missing; Imputed date = min (start date of study drug, 31DEC), if month and day are missing. If the end date is not missing and the imputed start date is after the end date, use the end date as the imputed start date. If both the start date and the end date are imputed and if the imputed start date is after the imputed end date, use the imputed end date as the imputation for the start date.

